#### **5.6.3 Adverse Drug Reaction Requiring Bintrafusp Alfa Discontinuation or Delays**

The following adverse reactions (ADRs) require permanent treatment discontinuation of bintrafusp alfa:

**Any Grade 4 ADRs require bintrafusp alfa treatment discontinuation** except for single laboratory values out of normal range that are unlikely related to trial treatment as assessed by the Investigator(s), do not have any clinical correlate, and resolve within 7 days with adequate medical management.

**Any Grade 3 ADRs require bintrafusp alfa treatment discontinuation** except for any of the following:

- Transient ( $\leq$ 6 hours) Grade 3 flu-like symptoms or fever, which is controlled with medical management
- Transient ( $\leq$ 24 hours) Grade 3 fatigue, local reactions, headache, nausea, or emesis that resolves to Grade  $\leq$ 1
- Single laboratory values out of normal range (excluding Grade  $\geq$ 3 liver function test increase) that are unlikely related to trial treatment according to the Investigator(s), do not have any clinical correlate, and resolve to Grade  $\leq$ 1 within 7 days with adequate medical management
- Tumor flare phenomenon defined as local pain, irritation, or rash localized at sites of known or suspected tumor
- Change in Eastern Cooperative Oncology Group Performance Status (ECOG PS) to 3 that

resolve to  $\leq 2$  within 14 days (infusions should not be given on the following cycle, if the ECOG PS is 3 on the day of trial drug administration)

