## **5.6 Bintrafusp Alfa Adverse Event Management**

### **5.6.1 Bintrafusp Alfa Adverse Events**

Based on the available preclinical data, pharmacological class effect, and periodic safety reviews, the following were considered as adverse events upon Bintrafusp Alfa infusion and classified as:

- Important identified risks
  - Infusion-related reaction (IRR) including hypersensitivity (immediate): Signs and symptoms may include but are not limited to pyrexia, chills, flushing, hypotension, dyspnea, wheezing, back pain, abdominal pain, and urticarial
  - Immune-related adverse events (irAEs) including colitis, pneumonitis/interstitial lung disease, endocrinopathies (thyroid disorders including hyperthyroidism, hypothyroidism, autoimmune thyroiditis and adrenal insufficiency), Type I diabetes mellitus, renal disorders (acute renal injury), hepatitis (increased transaminase), retinal micro-vasculitis, myositis, skin reactions like rash (generalized, maculopapular, erythematous, pemphigoid)
  - Skin lesions with hyperkeratosis, keratoacanthoma, cutaneous squamous cell carcinoma possibly due to TGF- $\beta$  inhibition.
- Important potential risks
  - Treatment related anemia
  - Alterations in wound healing, repair of tissue damage, or mucosal bleeding events
  - Embryofetal toxicities
- Non-important potential risk:
  - Mucosal bleeding

Mucosal bleeding events are a potential risk for M7824. Respective risk mitigation measures have been implemented in the protocol.

The following side effects have been observed in  $\geq 10\%$  of patients among 630 patients treated with bintrafusp alfa according to the results from two oncology clinical studies in patients with advanced solid tumors. Common side effects (reported in more than 1 in 10 people) include:

- Anemia (low number of red blood cells)
- Decreased appetite
- Fatigue
- Pruritis (itching)

- Dyspnea (shortness of breath)
- Constipation (difficulty passing stools)
- Nausea (feeling sick to the stomach)
- Pyrexia (raised body temperature)
- Asthenia (decreased muscle strength)
- Diarrhea (frequent loose, watery stools)
- Abdominal pain
- Vomiting
- Cough
- Headache
- Epistaxis (bleeding from the nose)
- Rash (maculo-papular rash)
- Aspartate aminotransferase increased (elevation of liver enzyme)
- Oedema peripheral (buildup of fluid in the body causing swelling)

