#### **5.6.2 Dose Modifications for Bintrafusp Alfa as Single Agent**

No dose reductions are permitted in this study, but doses may be omitted based on persisting toxicity. Any adverse event suspected to be immune-related should be managed according to the guidance for management of irAEs

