**Any Grade 2 ADR should be managed as follows:**

- If a Grade 2 ADR resolves to Grade  $\leq 1$  within 2 weeks treatment may continue
- If a Grade 2 ADR does not resolve to Grade  $\leq 1$  within 2 weeks, bintrafusp alfa should be held. If after another 2 weeks the event has not resolved to Grade 1, the patient should permanently discontinue treatment with bintrafusp alfa (except for hormone insufficiencies, that can be managed by replacement therapy; for these hormone insufficiencies, up to 2 subsequent doses may be omitted)
- Upon the second occurrence of the same Grade 2 ADR (except for hormone insufficiencies that can be managed by replacement therapy) in the same patient, treatment with bintrafusp alfa has to be permanently discontinued

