#### 5.6.5 Management of Immune-Related Adverse Events (IrAEs)

Because inhibition of PD-L1 by anti-PD-L1 component stimulates the immune system, bintrafusp alfa may cause toxicity by increasing the immune response, leading to inflammatory reactions collectively referred to as immune-related adverse events (irAEs).

Immune-related AEs are specific to immunotherapies and vary by organ system. Following immune-related AEs are important identified risks for bintrafusp alfa:

- Immune-related pneumonitis
- Immune-related hepatitis

- Immune-related colitis
- Immune-related nephritis and renal dysfunction
- Immune-related endocrinopathies
- (thyroid disorders, adrenal insufficiency, type 1 diabetes mellitus, pituitary disorders)
- Immune related rash
- Other immune-related events (myositis, myocarditis, encephalitis)

Following immune-related AEs are important potential risks for bintralusp alfa:

- Guillain-Barré syndrome
- Uveitis
- Pancreatitis
- Myasthenia gravis/myasthenic syndrome

Recommended guidance and management for specific irAEs are provided in the current NCCN guideline available at <http://www.nccn.org>.

Requirements in addition to NCCN guidelines:

- Permanent treatment discontinuation is required in case of immune-related Grade 4 rash/inflammatory dermatitis, nephritis, autoimmune hemolytic anemia, hemolytic uremic syndrome, aplastic anemia, immune thrombocytopenia, acquired thrombotic thrombocytopenic purpura inflammatory arthritis, myositis and polymyalgia-like syndrome.
- For Grade 4 immune-related lymphopenia, permanent treatment discontinuation will be required, if lymphopenia is considered immune-related in nature, no clear alternative explanation exists for the event, and it does not resolve within 14 days. Permanent treatment discontinuation is not required when the AE is manifested by a single laboratory value out of normal range without any clinical correlates. In this case, treatment should be held until the etiology is determined. If the event is not considered immune-related and resolves to Grade  $\leq 1$ , restarting treatment may be considered.
- For Grade 1 immune-related pneumonitis: continue treatment. If clinically indicated, monitor participants weekly or more frequently as needed with history, physical examination and pulse oximetry. If symptoms appear and/or changes in the physical exam are noted, treat as Grade 2.
- For myositis: in case of management with rituximab, treatment should be discontinued.

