#### **6.6.6 Methods of Recording Adverse Events**

- All AEs must be documented in the appropriate section of the CRF. An SAE report form (initial or follow up) must be completed in case of any of the seriousness criteria is met.
- The following aspects must be recorded for each event in the CRF:
  - A description of the AE in medical terms, not as reported by the subject;
  - The date of onset (start date)
  - The time of onset (start time)
  - The date of recovery (stop date)
  - The time of recovery (stop time)
  - The severity of the sign and/or symptom or clinically significant abnormal laboratory
  - Value according to NCI-CTCAE v.4. If no toxicity grade is described for a given sign, symptom or abnormal laboratory value, the Investigator(s) will grade the severity as mid (grade 1), moderate (grade 2), severe (grade 3), or life-threatening or disabling (grade 4).
  - Death (grade 5) as defined by NCI-CTCAE v.4 is mainly regarded as an outcome and will be documented accordingly (see below).
- The causal relationship to binrafusp alfa as assessed by the Investigator(s); the decisive factor in the documentation is the temporal relation between the AE and the study drug. The following judgments of the causality to study drug or study procedures are to be used:
  - Not Related = not suspected to be reasonably related to the

investigational product. AE could not medically (pharmacologically/ clinically) be attributed to the investigational product under study in this protocol

- Related = suspected to be reasonably related to the investigational product. AE could medically (pharmacologically/ clinically) be attributed to the investigational product under study in this protocol
- Action taken on binrafusp alfa (none, medication discontinued, dose reduction, medication delayed, reduction of infusion rate).
- Other action (none, concomitant medication given, new or prolonged hospitalization, procedural surgery).
- The outcome according to the following definitions:
  - Recovered without sequelae (AE disappeared)
  - Recovered with sequelae (AE has resulted in permanent disability/incapacity)
  - Not yet recovered
  - Not recovered at death
  - Change in toxicity grade/severity or seriousness (e.g., an AE with no change of toxicity grade but newly classified as an SAE due to hospitalization.
  - Fatal (AE resulted in death)

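### Section 5.6.3: an isolated liver-test rise judged unlikely related, without clinical correlate and gone within 7 days, must stop treatment at Grade 3 but is excepted at Grade 4

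*Protocol*

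**What the plan says.** Section 5.6.3 makes discontinuation the default at Grades 3 and 4 and then lists exceptions.

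- **Grade 4.** There is one exception. Discontinuation is required "except for single laboratory values out of normal range that are unlikely related to trial treatment as assessed by the Investigator(s"), provided the value also has no clinical correlate "and resolve within 7 days with adequate medical management". Liver tests are not mentioned.
- **Grade 3.** One of several exceptions covers the same kind of laboratory value, but its parenthesis takes out any Grade 3 or higher "liver function test increase) that are unlikely related to trial treatment according to the Investigator(s"). It also requires no clinical correlate, and recovery to Grade 1 or less within 7 days.
- **Grade 2.** If a first occurrence returns to Grade 1 or less "within 2 weeks treatment may continue".

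Section 5.6.2 adds the routing rule: "Any adverse event suspected to be immune-related should be managed according to the guidance for management of irAEs". It also rules out dose reductions. The hepatitis table in section 5.6.5 stops treatment permanently at both G3 and G4.

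**The concern.** A stopping rule for toxicity should not relax as severity rises. For liver tests, the Grade 3 wording takes the decision out of the investigator's hands: even a rise thought unlikely to be related ends treatment. The Grade 4 wording hands that judgement back at the more dangerous level.

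The attribution may well be wrong for this organ. Section 5.6.1 lists "Aspartate aminotransferase increased (elevation of liver enzyme") among the common side effects of the drug, and names hepatitis with raised transaminase among the important identified risks. If the judgement is wrong, a patient could be re-dosed after a Grade 4 liver value. The dose would be the full 1200 mg, because section 5.6.2 permits no reduction; the 50% reductions elsewhere in the protocol concern bleeding and falls in haemoglobin.

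**Working it through.** The protocol gives no figure to reproduce here. The check is to apply the rules to one event, changing only its grade.

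**The event.** An isolated liver-test rise, first occurrence, not suspected to be immune-related, judged unlikely related to treatment, without clinical correlate, and back to normal by day 7. Full normalisation satisfies any reading of resolution, so the unstated recovery grade in the Grade 4 sentence plays no part in the result.

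| Grade | Rule in 5.6.3 | Result |
|---|---|---|
| 2 | Back to Grade 1 or less within 2 weeks | Treatment may continue |
| 3 | Liver tests removed from the laboratory exception, so the default applies | Permanent discontinuation |
| 4 | Laboratory exception has no liver carve-out, and every stated condition is met | Excepted from discontinuation |

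The Grade 2 row is only context; the inversion lies between Grades 3 and 4.

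**Does another section close the gap?**

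1. *Hepatitis table, section 5.6.5.* It would stop treatment at G3 and G4, but section 5.6.2 sends only suspected immune-related events there. The event above is not one.
2. *Additional Grade 4 list, section 5.6.5.* It begins "Permanent treatment discontinuation is required in case of immune-related Grade 4 rash/inflammatory dermatitis, nephritis, autoimmune hemolytic anemia" and continues with other conditions. It is confined to immune-related events and names no liver test.
3. *Binary causality, section 6.6.6.* One category is defined as "Not Related = not suspected to be reasonably related to the" investigational product. One could argue that an unlikely-related value is recorded this way and is therefore no adverse drug reaction at any grade. But both laboratory exceptions apply only to values judged unlikely related. If such values fell outside 5.6.3, both exceptions would be empty, and so would the liver exclusion. The exclusion has effect only if these values remain within the section.
4. *Unacceptable toxicity, section 6.4.* This remains a ground for removal, but it is a matter of judgement and not a fixed stop.

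**Illustration.** The protocol prints AST/ALT bands only in the hepatitis table: 5–20 x ULN for G3 and above 20 x ULN for G4. Section 6.1 grades events by CTCAE version 4.0, so borrowing that cut-off is an assumption. On it, a rise to 19 x ULN must stop treatment and a rise to 21 x ULN is excepted. The inversion is the same wherever the cut-off lies.

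**Frequency.** Section 5.6.1 reports AST increase in at least 10% of 630 patients: 0.10 × 630 = 63 patients or more, of any grade. This shows only that liver signals occur with the drug. It gives no rate for Grade 3 or 4 values, and none is estimated here.

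**The case against.** The strongest reply is that this is a misplaced parenthesis with little practical reach. In a list that governs only Grade 3 events, the sign for 3 or higher does no work unless Grade 4 liver tests were also in mind, so the intended rule can be seen. The protocol treats raised transaminase as a recognised immune-related presentation, and mere suspicion is enough to send a case to the hepatitis table, which stops treatment at G4 and asks for a work-up of other causes from G2 upward. The gap opens only when the investigator does not suspect an immune cause, judges the rise unlikely related, finds no clinical correlate and sees it resolve within 7 days. Even then the exception permits re-dosing without compelling it, doses may be omitted for persisting toxicity, and liver function is checked every 2 weeks.

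Most of this stands as a limit on how often the gap matters. It does not remove the gap. The visible intent supports the correction, because a site must follow the Grade 4 sentence as printed. The other safeguards rest on investigator judgement, which is what the Grade 3 exclusion was written to override. The causality argument is a fair one, but it fails because it would leave both exceptions without content.

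**Conclusion.** The point holds as the text stands. With all else equal, the same liver-test event is a mandatory permanent stop at Grade 3 and is excepted at Grade 4. The conclusion rests on the printed wording of 5.6.3 and on reading unlikely-related values as still within that section, which is the only reading that gives the exceptions any effect. It does not depend on the borrowed 20 x ULN cut-off.

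The case needs several conditions to hold together and should be rare. No endpoint, sample size or error rate is affected. It should nevertheless be corrected, because it is a mandatory patient-safety rule and the correction restores what the Grade 3 wording indicates was intended.

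**What to change.** In the Grade 4 sentence of section 5.6.3, insert the parenthesis (excluding liver function test increase) directly after the reference to laboratory values outside the normal range. The Grade 3 and Grade 4 rules then agree.

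As a separate clarification, state in the same sentence what recovery is meant by resolving within 7 days. It should be no looser than the Grade 1 or less required at Grade 3; if full normalisation is intended, say so and keep it.

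The cost is a few words in one sentence, by protocol amendment, with no extra patients, visits or tests.

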G1: Symptoms do not affect the quality of life or controlled with topical regimen and/or oral antipruritic	
Continue ICPi
 
Treat with topical emollients and/or mild-moderate potency topical corticosteroids
 
Counsel patients to avoid skin irritants and sun exposure

G2: Inflammatory reaction that affects quality of life and requires intervention based on diagnosis	
Consider holding ICPi and monitor weekly for improvement. If not resolved, interrupt treatment until skin AE has reverted to Grade 1
 
Consider initiating prednisone (or equivalent) at dosing 1 mg/kg, tapering over at least 4 weeks
 
In addition, treat with topical emollients, oral antihistamines, and medium- to high-potency topical corticosteroids

G3: As G2 but with failure to respond to indicated interventions for a G 2 dermatitis	
Hold ICPi therapy and consult with dermatology to determine appropriateness of resuming
 
Treat with topical emollients, oral antihistamines, and high-potency topical corticosteroids
 
Initiate (methyl)prednisolone (or equivalent) 1-2 mg/kg, tapering over at least 4 weeks

G4: All severe rashes unmanageable with prior interventions and intolerable	
Permanently discontinue ICPi
 
Systemic corticosteroids: IV (methyl)prednisolone (or equivalent) dosed at 1-2 mg/kg with slow tapering when the toxicity resolves

1.0 Skin Toxicities	
	
Monitor closely for progression to severe cutaneous adverse reaction
 
Should admit patient immediately with direct oncology involvement and with an urgent consult by dermatology

1.2 Bullous dermatoses	

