G3: Increase of seven or more stools per day over baseline, incontinence, hospitalization indicated, severe increase in ostomy output compared with baseline, limiting self-care ADL	
Should consider permanently discontinuing CTLA-4 agents and may restart PD-1, PD-L1 agents if patient can recover to G1 or less.
 
Administer corticosteroids (initial dose of 1-2 mg/kg/d prednisone or equivalent)
 
Consider hospitalization or outpatient facility for patients with dehydration or electrolyte imbalance
 
If symptoms persist <math>\geq 3-5</math> days or recur after improvement, consider administering IV corticosteroid or noncorticosteroid (eg, infliximab)
 
Consider colonoscopy in cases where patients have been on immunosuppression and may be at risk for opportunistic infections as an independent cause for diarrhea (ie, CMV colitis) and for those who are anti- TNF or corticosteroid refractory

G4: Life-threatening consequences; urgent intervention indicated	
Permanently discontinue treatment Should admit patient when clinically indicated; patients managed as outpatients should be very closely monitored Administer 1-2 mg/kg/d methylprednisolone or equivalent until symptoms improve to G1, and then start taper over 4-6 weeks Consider early infliximab 5-10 mg/kg if symptoms refractory to corticosteroid within 2-3 days Consider lower GI endoscopy if symptoms are refractory despite treatment or there is concern of new infections

Additional considerations
 
The use of vedolizumab (not approved in Japan) may be considered in patients refractory to infliximab and/or contraindicated to TNF-<math>\alpha</math> blocker. The decision should be made on an individual basis from gastroenterology and oncology evaluation. This is based on case series showing promising results
 
Patients with hepatitis and irAE colitis are rare, and management should include permanently discontinuing ICPI and offering other immunosuppressant agents that work systemically for both conditions
 
Currently, enteritis alone as the cause of diarrhea is uncommon and requires small bowel biopsy as the evaluation tool. It may be managed similar as colitis, including corticosteroid and/or infliximab, etc
	

3.0 GI Toxicities	
3.2 Hepatitis	

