***MANAGEMENT OF ENDOCRINE irAES IN PATIENTS TREATED WITH ICPis***

5.0 Endocrine Toxicity	
Counsel patients to inform their health care provider immediately if they experience any changes in their health since their last visit, especially any of the following:	
Headaches that will not go away or unusual headache patterns Vision changes Rapid heartbeat Increased sweating Extreme tiredness or weakness Muscle aches Weight gain or weight loss Dizziness or fainting Feeling more hungry or thirsty than usual Hair loss Changes in mood or behavior, such as decreased sex drive, irritability, or forgetfulness Feeling cold Constipation Voice gets deeper Urinating more often than usual Nausea or vomiting Abdominal pain	
5.1 Thyroid	
5.1.1 Primary hypothyroidism	
Definition: Elevated TSH, normal or low FT4 Diagnostic work-up TSH and FT4 every 4-6 weeks as part of routine clinical monitoring on therapy or for case detection in symptomatic patients	
Grading	
Management	

M7824 Clinical Protocol v2.0 dated 01-Dec-2021

G1: TSH < 10 mIU/L and asymptomatic
 
G2: Moderate symptoms; able to perform ADL; TSH persistently > 10 mIU/L
	
Should continue ICPi with close follow-up and monitoring of TSH, FT4 May hold ICPi until symptoms resolve to baseline
 
Consider endocrine consultation
 
Prescribe thyroid hormone supplementation in symptomatic patients with any degree of TSH elevation or in asymptomatic patients with TSH levels that persist > 10 mIU/L (measured 4 weeks apart)
 
Monitor TSH every 6-8 weeks while titrating hormone replacement to normal TSH FT4 can be used in the short term (2 weeks) to ensure adequacy of therapy in those with frank hypothyroidism where the FT4 was initially low
 
Once adequately treated, should monitor thyroid function (at least TSH) every 6 weeks while on active ICPi therapy or as needed for symptoms to ensure appropriate replacement; repeat testing annually or as indicated by symptoms once stable

G3-4: Severe symptoms, medically significant or life- threatening consequences, unable to perform ADL
	
Hold ICPi until symptoms resolve to baseline with appropriate supplementation
 
Endocrine consultation

5.0 Endocrine Toxicity	
	May admit for IV therapy if signs of myxedema (bradycardia, hypothermia) Thyroid supplementation and reassessment as in G2

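### Section 5.6.3 makes Grade 3 and 4 drug reactions permanent stops with no immune-related exception, the Section 5.6.5 tables hold and resume for some of the same events, and no precedence is stated

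*Protocol*

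**What the plan says.** Section 5.6.3 opens with the consequence, "The following adverse reactions (ADRs) require permanent treatment discontinuation of bintrafusp alfa", and then gives two general rules: "Any Grade 4 ADRs require bintrafusp alfa treatment discontinuation" and "Any Grade 3 ADRs require bintrafusp alfa treatment discontinuation".

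- The Grade 4 rule has one exception: an isolated laboratory value judged unlikely to be treatment-related, without clinical correlate, that resolves within 7 days.
- The Grade 3 rule has five: brief flu-like symptoms or fever; brief fatigue, local reaction, headache, nausea or emesis; isolated laboratory values judged unlikely to be related, but not liver test increases of Grade 3 or higher; tumor flare; and a temporary fall to ECOG 3.
- The Grade 2 rules that follow carve out one immune-type group: "except for hormone insufficiencies, that can be managed by replacement therapy".

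Section 5.6.2, immediately before, says: "Any adverse event suspected to be immune-related should be managed according to the guidance for management of irAEs". It sets no grade limit and does not mention 5.6.3.

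The organ tables in Section 5.6.5 give their own actions by grade. For Grade 3-4 primary hypothyroidism: "Hold ICPi until symptoms resolve to baseline with appropriate supplementation". For Grade 3 rash: "Hold ICPi therapy and consult with dermatology to determine appropriateness of resuming". For Grade 3 colitis, investigators "may restart PD-1, PD-L1 agents if patient can recover to G1 or less". Section 5.6.5 also names certain Grade 4 immune-related events that require a permanent stop; no endocrine event is on that list.

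**The concern.** Section 5.6.5 attributes immune-related events to PD-L1 inhibition by the study drug. An event judged immune-related is therefore also an adverse drug reaction, and at Grade 3 or 4 it falls within the literal scope of 5.6.3 as well as the tables. If the two texts give different actions and neither yields, two investigators who both follow the protocol can treat the same patient differently.

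Patient safety comes first. The second stake is the data. Toxicity and tolerability are a secondary objective (Section 2.2), and Section 6.6.6 requires the action taken on study drug to be recorded for each event. Whether an event is counted as a discontinuation or a delay would then partly reflect which section was consulted. With 38 patients planned, each patient handled differently moves the discontinuation proportion by 1/38 = 2.6 percentage points, if all 38 form the denominator.

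**Working it through.** No figure in the plan is at issue, so the check is a comparison of texts.

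**Step 1. Do the 5.6.3 exceptions reach the table events?** No. The clinical exceptions are brief symptoms, tumor flare and performance status. The laboratory exception requires the value to be unlikely related to treatment, which an event judged immune-related is not.

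**Step 2. Compare the actions.**

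| Event | Section 5.6.3 | Section 5.6.5 table | Relation |
|---|---|---|---|
| Hypothyroidism, hyperthyroidism, G3-4 | Permanent stop | Hold until symptoms are back to baseline on treatment | Conflict |
| Adrenal insufficiency, hypophysitis, G3-4 | Permanent stop | Hold until stable on replacement hormone | Conflict |
| Diabetes, G3-4 | Permanent stop | Hold until glucose is controlled and toxicity is G1 or lower | Conflict |
| Myositis, G3 | Permanent stop | Hold until G1 or lower; permanent stop if the heart is involved | Conflict without cardiac involvement |
| Immune thrombocytopenia, G3 | Permanent stop | Hold or interrupt until G1 | Conflict |
| Arthritis, polymyalgia-like syndrome, G3 | Permanent stop | Hold; may resume with rheumatology input | Resumption allowed, not required |
| Rash, colitis, G3 | Permanent stop | Resumption possible | Resumption allowed, not required |
| Hepatitis, pneumonitis, nephritis, G3 | Permanent stop | Permanent stop | Agree |

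The endocrine rows are the clearest, because they cover Grade 4 as well as Grade 3 and frame the action as a hold with a defined end.

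**Step 3. Does Section 5.6.2 settle it?** It directs suspected immune-related events to the irAE guidance. It does not say that 5.6.3 then ceases to apply, and 5.6.3 is not worded as subject to it.

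**Step 4. Is 5.6.3 confined to non-immune reactions?** Its own wording points the other way in two places.

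- The Grade 2 rules exempt hormone insufficiencies. Section 5.6.1 lists hypothyroidism and adrenal insufficiency among the immune-related events. If such events lay outside 5.6.3, the exemption would have little purpose. It is not repeated at Grade 3 or 4.
- The Grade 3 laboratory exception is withheld from liver test increases of Grade 3 or higher. Section 5.6.1 lists hepatitis with raised transaminases as immune-related.

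**Step 5. Is there a rule for the same event with two different numbers?** Yes, for Grade 4 lymphopenia. The 5.6.3 laboratory exception needs resolution within 7 days and an unlikely relation to treatment. Section 5.6.5 mandates a permanent stop only if the event is immune-related, lacks a clear alternative explanation and has not resolved within 14 days. As an illustration, an immune-related case resolving on day 10 is a permanent stop under 5.6.3 and not a mandated one under 5.6.5.

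**The case against.** The strongest defence is that the specific text governs the general one. Section 5.6.2 covers any suspected immune-related event at any grade and stands directly before 5.6.3, so 5.6.3 can be read as the rule for all other reactions. Section 5.6.5 supports this. Its list of named Grade 4 events requiring a permanent stop would be redundant if 5.6.3 already stopped every Grade 4 immune-related event, and its separate lymphopenia rule would serve no purpose. Several tables give Grade 3 and Grade 4 different actions in a way that looks deliberate. The hormone exemption in 5.6.3 is a Grade 2 provision and does not by itself show that the Grade 3 and 4 sentences override the tables.

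Most of this stands. It makes it likely that the tables were meant to govern, and a reader who inferred that Section 5.6.2 can be set aside, or that 5.6.3 must prevail, would go further than the text allows. It also stands that the rash and colitis rows are permissive: an investigator who stops permanently breaches neither text, so those rows are not opposite rules.

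What the defence does not supply is a statement of precedence. It asks the investigator to infer that a section about any Grade 3 or 4 drug reaction silently excludes immune-related ones, although that section addresses immune-type events itself.

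**Conclusion.** The point holds as a lack of internal consistency and of stated precedence. It is firmest for the five Grade 3-4 endocrine entries, where a hold with a defined end meets a permanent stop. It is weaker for the Grade 3 rows that only permit resumption, and absent where both texts already require a permanent stop.

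Two stronger readings are tempting and not supported.

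- **A patient count.** The protocol's Background cites Grade 3 or higher drug-related rates of 12.9% to 29.6%, and 0.129 × 38 = 4.9 and 0.296 × 38 = 11.2 suggest 5 to 11 patients. The upper rate comes from a pembrolizumab cohort; the cited bintrafusp alfa rates reach 25%, or 0.25 × 38 = 9.5. More importantly, these rates count all drug-related events, including anemia, cystitis and gastroparesis, and some immune-related Grade 3 events are permanent stops under both texts. The number in conflict cannot be derived.
- **An effect on ORR or PFS.** A reader might infer one through exposure, but the protocol gives no basis for sizing or showing it. Note k to the Schedule of Assessments continues imaging after a stop without radiographic progression, until progression or alternate therapy.

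The conclusion rests on one assumption: that an event judged immune-related counts as an adverse drug reaction under 5.6.3. It takes no position on which rule is clinically right.

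**What to change.** Reconcile Sections 5.6.2 and 5.6.3 with the additional requirements and tables in Section 5.6.5. State in 5.6.3 which text takes precedence for immune-related Grade 3 and Grade 4 events, and bring the exception lists and table rows into line with that statement, starting with the endocrine rows and Grade 4 lymphopenia. Which rule applies to each event is the sponsor's clinical decision.

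The cost is an amendment to protocol wording. It adds no visits, procedures or data collection, and changes neither the sample size nor the planned analyses.
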